12.4.1.2 Secondary efficacy endpoints

All statistical analyses to be performed on the secondary efficacy endpoints will be based on the FAS of the respective period.

12.4.1.2.1 Key secondary efficacy endpoints

The key secondary endpoints (see [Section 12.3.1.2.1](#)) will be tested with ANCOVA models similar to that for the primary analysis of the primary endpoint (see [Section 12.4.1.1](#)). However, the study baseline of the analyzed TETRAS subscale will be used for baseline adjustment. Missing data handling, sensitivity analyses and pooling of study sites will also be handled analogously to the primary endpoint analysis.

Multiplicity adjustments are addressed in [Section 12.4.7.5](#).

12.4.1.2.2 Other secondary efficacy endpoints

Other secondary endpoints (see [Section 12.3.1.2.2](#)) will be analyzed for observed cases.

Unilateral treatment period:

Other secondary endpoints of the unilateral treatment period will be analyzed by applying ANCOVA models similar to that for the primary analysis of the primary endpoint (see [Section 12.4.1.1](#)). However, for TETRAS subscales, the study baseline of the analyzed TETRAS subscale will be used for baseline adjustment. For GICS by investigator and subject, the study baseline of the TETRAS ADL total score will be used for baseline adjustment.

Bilateral treatment period:

Endpoints of Category A (see [Section 12.4.1](#)) will be analyzed by applying ANCOVA models similar to that for the primary analysis of the primary endpoint (see [Section 12.4.1.1](#)). However, the Cycle 2 baseline of the analyzed variable will be used for

baseline adjustment. If no such baseline exists (e.g., GICS), the Cycle 2 baseline of the TETRAS ADL total score will be used for baseline adjustment.

Endpoints of Category B (see [Section 12.4.1](#)) will be analyzed by a repeated measures model. For that purpose the UL (dominant/non-dominant) will be added as repeated effect to the ANCOVA model. The covariance structure will be unspecified and allow to differ for the treatment groups.

The above mentioned ANCOVA models will be used to estimate the average changes from baseline by least-square means and respective 95% confidence intervals by UL and overall.

12.4.1.3 Other efficacy endpoints

Other efficacy endpoints will be analyzed by descriptive statistics only.

12.4.2 Pharmacodynamic endpoints

Not applicable.

12.4.3 Pharmacokinetic endpoints

Not applicable.

12.4.4 Pharmacogenetic endpoints

Not applicable.

12.4.5 Safety endpoints

If not otherwise specified, safety endpoints will be evaluated by treatment group (e.g. for AEs). All safety endpoints will be analyzed separately for the unilateral (SES-UP) and bilateral (SES-BP) treatment period, and by UL, where appropriate. Analyses for the unilateral phase and the total study duration will be based on the SES-UP while analyses for the bilateral phase will be based on the SES-BP.

AEs will be coded according to the Medical Dictionary for Regulatory Activities [MedDRA] version that is in effect at the time the database is closed. Only TEAEs will be analyzed, which are defined as AEs with onset or worsening after the first administration of the IP.

If in case of a public health emergency, e.g. due to a COVID-19 outbreak, the second injection visit V8a of Cycle 2 is performed later than 25 weeks after the first injection visit V2 the AEs starting or worsening later than 25 weeks after baseline visit V2 of Cycle 1 and before injection at V8a of Cycle 2 are treated as non-TEAEs.

12.4.5.1 *Primary safety endpoint*

No primary safety endpoint has been defined.

12.4.5.2 *Secondary safety endpoints*

See [Section 12.3.5.2](#) for definition of the secondary safety endpoint. Frequency tables will be provided for incidences:

- by MedDRA system organ class (SOC) and preferred term (PT) level;
- by treatment group and, in addition for the bilateral phase, overall; and
- by treatment cycle and total study duration.

12.4.5.3 *Other safety endpoints*

See [Section 12.3.5.3](#) for definition of the other safety endpoints.

- Exposure to study drug will be summarized descriptively by muscle and overall. This will be provided by treated UL (unilateral phase: dominant arm; bilateral phase: dominant and non-dominant arm). Moreover, the total exposure by subject will be summarized;
- Incidences of TEAEs, TEAEs of special interest [TEAESIs], serious TEAEs, and TEAEs leading to discontinuation, and COVID-19 related TEAEs will be presented by MedDRA SOC and PT and by treatment group and, in addition for the bilateral phase, overall;
- Global assessment of tolerability scale as assessed at Week 24 of unilateral treatment period will be summarized descriptively by treatment group. Week 12 of bilateral treatment period will be summarized descriptively by treatment group and overall. This includes frequency tables and statistics for continuous variables;
- Absolute values of HHD grip strength testing and changes from applicable cycle baseline to all applicable post-baseline visits will be summarized descriptively by treated UL. In addition, for the unilateral phase the intra-individual difference of changes from baseline between body sides will be summarized;

- 

- Time courses of vital signs (blood pressure, pulse rate) and body weight measurement at selected visits and changes from applicable cycle baseline will be summarized descriptively; and
- Time courses of standard clinical chemistry and hematology parameters measurement at selected visits and changes from applicable cycle baseline will be summarized descriptively.

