5. No treatment with parenterally administered drugs that interfere with neuromuscular transmission (e.g., intrathecal baclofen, tubocurarine-type muscle relaxants used in anaesthesia), aminoquinolines, or local anesthetics in the treated region within two weeks before the study resumption or intended to be administered during the study.	Efficacy, safety
6. Women of childbearing potential ^b must be using a highly effective method of birth control ^c and must be willing to continue using this during the entire study period.	Safety
7. Understanding of study procedures and willingness to abide by all procedures during the course of the study.	Administrative
8. No acute COVID-19; no COVID-19 or positive SARS-CoV-2 test indicative of an acute infection or symptoms suspicious of COVID-19 (e.g. fever, tiredness, dry cough) in the past 14 days.	Safety
9. Combined agreement of subject and investigator on the subject's potential benefit from study treatment of both ULs.	Efficacy, safety
10. Visible tremor of both ULs as assessed by the investigator on TETRAS Performance subscale item 4 with a score of ≥ 1.5 in either the forward horizontal reach posture, and/or lateral 'wing beating' posture and/or finger-nose(chin)-finger movement.	Efficacy
11. Body weight ≥ 50 kg.	Safety
12. Negative pregnancy test (for females of childbearing potential).	Safety

13. Absence of any infection or inflammation in the areas of the planned injection sites.	Safety
14. Absence of medically relevant, severe, or any serious AEs that are judged to have a causal relationship to the study treatment.	Safety
15. For subjects on coumarins or other anticoagulants monitored by INR, the investigator confirms and documents that the subject has an INR value of ≤ 2.5 . For subjects on direct thrombin inhibitors, factor Xa inhibitors, heparin or heparinoids, the investigator confirms and documents that the therapy has remained unchanged since screening (V1) or that the subject has an aPTT time ≤ 80 seconds.	Safety

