9.1.1.3.1 Adverse events

AEs will be recorded in source documents after the ICF has been signed and will be recorded in the eCRF at all successive visits.

Subjects are requested to report all AEs to the investigator or site staff. It is the obligation of the investigator to detect AEs by questioning the subject at each visit. At the injection visits, AE questioning will be done twice; first before injection and the second assessment will be performed about 30 minutes after injection. All AEs observed throughout the course of the study are to be documented in the subject file and in the eCRF. This equally applies to AEs during the period of a potential COVID-19 related temporary halt. For definitions and details regarding documentation and reporting of AEs, see [Sections 10.1 to 10.3](#).

Subjects will be actively questioned and closely monitored for signs of potential toxin spread as indicated by specific AESIs, defined by the European Medicines Agency and FDA, see [Section 10.3](#) and [Table 7](#). The investigator or delegate must actively question each subject for AESIs, see [Section 10.3](#) and [Table 7](#), at each visit, beginning at the study baseline visit (V2) before injection and approximately 30 minutes after injection. Questioning at baseline before injection is done to identify possible concomitant diseases which have not been recorded as medical history. The questioning and documentation of answers will be standardized.

If any contact with the subject identifies an (S)AE/AESI that needs confirmation or treatment, (e.g. respiratory disorder, dyspnea, aspiration, dysphagia, speech disorder, dysphonia, other signs of bulbar palsy, or botulism) the investigator must schedule an extra visit as soon as possible after the contact. If such an extra visit is not possible in case of a public health emergency, e.g. due to a COVID-19 outbreak, it is up to the medical

judgement of the investigator to decide whether referral to a specialist or emergency care is necessary for further treatment and confirmation.

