2.2.2.2 Secondary Safety Endpoint

The secondary safety endpoint for both the unilateral and bilateral treatment period will be the following:

- Incidence of treatment-emergent AEs [TEAEs] related to treatment as assessed by the investigator.

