4.5 Safety Analyses

All safety analyses for Cycle 1 will be performed by actual treatment group on SES-UP. All safety analyses for Cycle 2 will be performed on the SES-BT, by actual treatment group in Cycle 1 and in total. All safety analyses for the total observation period will be performed on SES-UP, by actual treatment group in Cycle 1 and in total.

For calculation of TEAE based incidence rates, the denominator will be the number of subjects in the respective analysis set, by actual treatment group or in total (as applicable).

AEs will be coded according to the Medical Dictionary for Regulatory Activities [MedDRA] version that is in effect at the time the database is closed.

Only TEAEs will be analyzed, which are defined as AEs with onset or worsening after the first administration of the IP. For details on separation of TEAEs and non-TEAEs see [Appendix 8.5](#).

If in case of a public health emergency, e.g. due to a COVID-19 outbreak, the second injection visit V8a of Cycle 2 is performed later than 25 weeks after the first injection visit V2 the AEs

¹⁷ Health state = pattern of scores over the five dimensions, e.g., 13333 for a subject indicating slight problems in mobility and severe problems on the other four dimensions.

starting or worsening later than 25 weeks after baseline visit V2 of Cycle 1 and before injection at V8a of Cycle 2 are treated as non-TEAEs.

If an AE worsens between start and end of this AE, it will be considered as new AE entry with a new record in the SDTM dataset starting with the date of the worsening (start of new AE = worsening date, stop date of milder AE episode = date of AE worsening).

For analysis, incompletely recorded or completely missing start of AEs will be estimated according to rules laid down in [Appendix 8.6](#). End dates will not be imputed. In the AE listing, start date as recorded and as imputed for analysis will be displayed.

Calculation of time to onset/duration of AEs (days):

- Time to onset of an AE is defined as start date of AE - date of first administration of study drug in respective treatment cycle [+ 1 day for TEAEs]
- The duration of an AE will be calculated as stop date - onset date + 1 day. The duration of an AE will be missing if no AE stop date is provided

Treatment-relatedness of AEs will be determined based on the assessment of the investigator.

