| Hemiparesis | Vision blurred |
| Hypoglossal nerve paresis | Vocal cord paralysis |
| Hyporeflexia | Vocal cord paresis |
| Hypotonia | |
| *LLT Extraocular muscle paresis, PT: Ophthalmoplegia Wording of terms is according to MedDRA version 26.1. | |

TEAEs of Cycle 1 are defined as TEAEs with onset or worsening before date and time of administration of IP at V8(a). For subjects who do not receive study treatment during Cycle 2 all TEAEs will be considered as TEAEs of Cycle 1. TEAEs of Cycle 2 are defined as TEAEs with onset or worsening on or after date and time of the administration of IP at V8(a).

In case of missing intensity or missing causal relationship of an AE to treatment, the worst-case principle will be applied, i.e., a missing intensity will be set to “severe” and a missing causal relationship will be set to “related”. Missing outcome will be set to “unknown”.

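### After an emergency-delayed V8a, AEs between Week 25 and the V8a injection are non-TEAEs only for subjects who resume, so whether a late event is counted depends on a later event

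*Protocol*

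**What the plan says.** SAP 4.5 sets the general rule: "Only TEAEs will be analyzed, which are defined as AEs with onset or worsening after the first administration of the IP". Protocol 12.4.5 has the same rule. Both documents then add an exception for a public health emergency. It is triggered when "the second injection visit V8a of Cycle 2 is performed later than 25 weeks after the first injection visit V2", and it covers AEs "starting or worsening later than 25 weeks after baseline visit V2 of Cycle 1 and before injection at V8a of Cycle 2". In the protocol's words, AEs arising after that limit and "before injection at V8a of Cycle 2 are treated as non-TEAEs". Neither text exempts events judged related or serious.

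For subjects without a second injection, SAP 4.5 gives no upper time limit: "For subjects who do not receive study treatment during Cycle 2 all TEAEs will be considered as TEAEs of Cycle 1".

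The only secondary safety endpoint (SAP 2.2.2.2, Protocol 12.3.5.2) is "Incidence of treatment-emergent AEs [TEAEs] related to treatment as assessed by the investigator". Protocol 9.1.1.3.1 requires AE documentation throughout the study and says of a halt: "This equally applies to AEs during the period of a potential COVID-19 related temporary halt". The events in question are therefore collected.

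**The concern.** Treatment emergence should be decided by when an event starts or worsens relative to dosing. Here it also depends on whether the subject is injected again later. Two subjects on the same hold with the same related event in Week 26 are handled differently if one resumes and the other does not.

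Resumption is not independent of safety. Protocol 7.4.1, criterion 14, requires "Absence of medically relevant, severe, or any serious AEs that are judged to have a causal relationship to the study treatment", so the subjects whose gap events are removed have been selected for the absence of the worst related events.

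What is at stake is the completeness of the related-TEAE, AESI and serious-TEAE summaries. Any effect on incidence is downward. Milder related events matter in this trial. Protocol 4.3 reports finger weakness as an adverse drug reaction in two NT 201 subjects (10.5%) of the predecessor study, with all reactions mild, and muscular weakness is on the AESI list.

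**Working it through.** **The cut-off.** V8 is planned for day 168 with a window of ±7 days (Protocol 9.2, Table 5). 168 + 7 = 175 days, and 175 / 7 = 25 weeks. The 25-week limit is therefore the end of the permitted V8 window, which makes it a reasonable end for Cycle 1 follow-up.

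**Who is covered.** The table applies the rules to an event that starts after Week 25 while the subject is on hold and before any V8a injection.

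| Event in the gap | Subject later injected at V8a | Subject never treated in Cycle 2 |
|---|---|---|
| Related; not serious, severe or medically relevant | Non-TEAE: out of the secondary endpoint, and out of the TEAESI tables if an AESI term | Cycle 1 TEAE, counted |
| Related and serious, severe or medically relevant | Normally does not arise, because criterion 14 bars resumption and the subject is discontinued | Counted |
| Unrelated, serious, not fatal | Non-TEAE: out of the serious-TEAE tables and the Section 14.3 listing | Counted |
| Fatal | Cannot arise, as there is no V8a injection | Counted |

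The first and third rows show the inconsistency.

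**Events against follow-up.** SAP 4.5.3 also plans TEAE tables for the total observation period. SAP 4.6.1 runs that period from first injection to last contact, last visit or last AE start, so it includes the gap. SAP 4.5 takes as denominator all subjects in the safety set. The reported follow-up and the denominator thus include the gap, while the resumers' events in it do not appear.

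**Size per subject.** Protocol 7.1 plans about 50 NT 201 and 25 placebo subjects. One subject is 1/50 = 2.0 percentage points or 1/25 = 4.0 points. These are maxima. The incidence counts subjects with at least one event, so a subject with another related Cycle 1 TEAE does not change it.

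**Expected size.** The documents give neither the number of V8a subjects nor an AE rate after Week 25, so the following rests on assumptions. Let k NT 201 subjects resume through V8a, and let p be the probability that a resumer's only related Cycle 1 event falls in the gap. Expected loss = k × p subjects, or 100 × k × p / 50 percentage points.

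| k | p = 2% | p = 5% | p = 10% |
|---|---|---|---|
| 0 | 0 | 0 | 0 |
| 5 | 0.1 subjects (0.2 points) | 0.25 (0.5) | 0.5 (1.0) |
| 10 | 0.2 (0.4) | 0.5 (1.0) | 1.0 (2.0) |
| 25 | 0.5 (1.0) | 1.25 (2.5) | 2.5 (5.0) |

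**The case against.** The strongest reply is that the rule is a sensible cap that touches little of importance. It coincides with the end of the planned V8 window. During a halt, Protocol 7.5.1 and 8.3 allow other botulinum toxin once the end-of-Cycle 1 visit is done, so a late event may follow non-study toxin. Nothing is lost from the record: SAP 4.5.3 provides a by-subject listing of every AE, emergent or not, for CSR Section 16.2, and expedited SAE and AESI reporting does not depend on TEAE status.

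Most of this stands. A cap at 25 weeks is defensible, but then it should apply to everyone, and non-resumers have no cap. Other toxin is a plausible reason, though the documents do not state it, and it would concern only subjects who received it. A listing does not replace inclusion in the incidence tables.

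A reader might infer three stronger things that the documents do not support:
- *Serious related events vanish from the endpoint.* As a rule they do not, because criterion 14 stops resumption and the exception then never applies. One ambiguity remains. Section 7.4.1 allows a single re-assessment after an acute event has resolved, and does not say whether a resolved related event still bars resumption.
- *Deaths are omitted.* A death in the gap precludes V8a, so it stays a TEAE and stays in the death listing.
- *The randomized comparison is biased in favor of NT 201.* The rule and the resumption criteria are the same for both arms, and no difference in resumption between arms can be shown from the documents.

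**Conclusion.** The point holds as a narrow, contingent inconsistency. When V8a is delayed beyond 25 weeks, resumers' gap events leave the TEAE analysis and non-resumers' equally late events stay in. For resumers, the losses are milder related events (secondary endpoint), AESIs such as non-severe muscular weakness (TEAESI tables), and unrelated serious events (serious-TEAE tables and Section 14.3 listing). The last group cannot affect the secondary endpoint, which counts related events only.

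The size cannot be computed and is zero if no subject used V8a. The ceiling is 2 points on NT 201 or 4 on placebo per affected subject, assuming the planned group sizes of 50 and 25. The predecessor study lasted 24 weeks and so gives no rate for events after Week 25. The conclusion also rests on the main text of SAP 4.5: Appendix 8.5, cited there for the separation of TEAEs from non-TEAEs, was not available, and further detail in it cannot be excluded. This is a worthwhile clarification, not a threat to the trial's conclusions.

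**What to change.** In Protocol 12.4.5, SAP 4.5 and SAP Appendix 8.5:

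1. Apply the same 25-week cut-off to resumers and non-resumers in the Cycle 1 TEAE tables, so that classification depends only on onset or worsening time.
2. Include gap AEs of both groups in the total-observation-period TEAE tables and in the Section 14.3 serious-TEAE and TEAESI listings.
3. Add one table of gap AEs by relatedness and seriousness, flagging subjects who received other botulinum toxin in the gap.
4. Record the change in SAP Section 6.

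The cost is one derivation flag, one extra table and some wording. The downside is that some late events that may not be due to study drug will appear in the total-period output. The flag for other toxin and the split by relatedness let the reader judge them.

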12.4.6 Other endpoints

Subject disposition, demographic data and baseline characteristics will be presented by using standard descriptive statistics.

Frequencies of concomitant treatments will be given by Anatomical Therapeutic Chemical classification system of the World Health Organization code level. Indications for concomitant therapies will not be coded and will only be listed. Medical history and concomitant diseases will be described on the basis of MedDRA system organ classes and preferred terms levels.

12.4.7 Special statistical/analytical issues

12.4.7.1 Discontinuations and missing data

Reasons for premature discontinuation of a subject's study participation will be summarized descriptively. If the premature discontinuation is related to a public health emergency, e.g. due to a COVID-19 outbreak, this information will be documented and listed (see also [Section 11.2](#)).

Details of handling of missing data for primary and key secondary endpoints are specified in [Section 12.4.1.1](#) and [Section 12.4.1.2.1](#). Other analyses will be based on observed case.

In general, discontinued subjects will not be replaced. In case of unforeseen higher number of missing data of important efficacy data (like Change from study baseline to Week 6 in maximum tremor amplitude measurement at wrist level, in TETRAS Performance dominant UL Score, or in TETRAS ADL UL score), 10% or higher in case of a public health emergency, e.g. due to a COVID-19 outbreak, additional subjects can be enrolled for this study in order to have up to 75 evaluable subjects for efficacy analysis. It is not expected that the total number of randomized subjects will be increased to more than 100. General circumstances potentially related to a public health emergency which are independent of study treatment will result in missing values at completely random (e.g. site closed for study subjects, site decided to perform virtual visit due unfavorable epidemiological situation, subject refused to come to site due unfavorable epidemiological situation, curfew or restricted travel). Only for these missing values completely at random due circumstances of a public health emergency additional subjects will be randomized. For missing values which are potentially also related to study treatment or which are not

related to a public health emergency, no additional subjects will be randomized. In this approach of randomization of additional subjects only in case of missing values completely at random the type one error is not affected. The decision about recruitment of additional subjects will be made by Merz study team under double blind conditions.

